6.1.6 Pregnancy

Pregnancy in a study subject or a partner of a study subject must be reported to AbbVie within 1 working day of the site becoming aware of the pregnancy. Subjects who become pregnant during the study must be discontinued (Section 5.4). Pregnancies in study subjects and their partners will be collected from the date of the first dose through 180 days following the last dose of study drug.

Information regarding a pregnancy occurrence in a study subject or a study subject's partner and the outcome of the pregnancy will be collected. In the event of pregnancy occurring in a subject's partner during the study, written informed consent from the partner must be obtained prior to the collection of any such information.

Pregnancy in a study subject is not considered an AE. However the medical outcome of an elective or spontaneous abortion, stillbirth or congenital anomaly is considered a SAE and must be reported to AbbVie within 24 hours of the site becoming aware of the event.

6.1.7 Toxicity Management

Adalimumab

Subjects who develop a new infection while undergoing treatment with adalimumab should be monitored closely. Administration of study injections should be interrupted if a subject develops an infection requiring IV anti-infective treatment or if an infection meets the definition of "serious" (see Section 6.0 for definitions). Study medication may be restarted once the physician determines that the infection has been successfully treated. Otherwise prohibited concomitant medications may be given if medically necessary.

Prior to use, every attempt should be made to contact the AbbVie Study Physician for direction on re-introduction of adalimumab therapy after prohibited medication administration.

If the subject must undergo elective surgery, the study injections must be interrupted 2 weeks prior to the surgery. If the subject must undergo emergency surgery, the study injections must be interrupted at the time of the surgery. The injectable study medication can recommence at least 2 weeks after surgery once the physician has examined the surgical site and determined that it has healed and there is no sign of infection.

Methotrexate

The definition of MTX intolerance and/or toxicity is based on MTX intolerance and toxicity as described in the MTX prescribing information provided to the investigator. An event of intolerance or toxicity is to be recorded as AE. The decision for treatment adjustment is at the investigator's discretion.

MTX will be escalated by 5.0 mg every 2 weeks. If MTX intolerance/toxicity is suspected, MTX dose reduction by 5 mg, including during the escalation period, may be performed. Any subject who cannot tolerate the highest recommended dose specified in the protocol (20-25 mg ew) due to toxicity or intolerance, is permitted to continue on the highest tolerable dose.

Temporary MTX discontinuation followed by re-introduction/re-escalation of MTX is allowed if the issue resolves within 4 weeks. The TA MD must be consulted if the Investigator would like to temporarily discontinue MTX more than one time.

If the investigator would like to decrease the MTX dose for any reasons other than MTX intolerance/toxicity, the AbbVie TA MD must be contacted first.

6.2 Product Complaint

6.2.1 Definition

A Product Complaint is any Complaint (see Section 6.0 for the definition) related to the biologic or drug component of the product or to the medical device component(s).

For a product this may include, but is not limited to, damaged/broken product or packaging, product appearance whose color/markings do not match the labeling, labeling discrepancies/inadequacies in the labeling/instructions (example: printing illegible), missing components/product, device not working properly, or packaging issues.

For medical devices, a product complaint also includes all deaths of a subject using the device, any illness, injury, or adverse event in the proximity of the device, an adverse event that could be a result of using the device, any event needing medical or surgical intervention including hospitalization while using the device and use errors.

Any information available to help in the determination of causality by the device to the events outlined directly above should be captured.

6.2.2 Reporting

Product Complaints concerning the investigational product and/or device must be reported to the Sponsor within 24 hours of the study site's knowledge of the event via the Product Complaint form. Product Complaints occurring during the study will be followed-up to a satisfactory conclusion. All follow-up information is to be reported to the Sponsor (or an authorized representative) and documented in source as required by the Sponsor. Product Complaints associated with AEs will be reported in the study summary. All other complaints will be monitored on an ongoing basis.

Product Complaints may require return of the product with the alleged complaint condition (syringe, pen, etc.). In instances where a return is requested, every effort should be made by the investigator to return the product within 30 days. If returns cannot be

accommodated within 30 days, the site will need to provide justification and an estimated date of return.

The description of the complaint is important for AbbVie in order to enable AbbVie to investigate and determine if any corrective actions are required.

7.0 Protocol Deviations

AbbVie does not allow intentional/prospective deviations from the protocol unless when necessary to eliminate an immediate hazard to study subjects. The principal investigator is responsible for complying with all protocol requirements, and applicable global and local laws regarding protocol deviations. If a protocol deviation occurs (or is identified) after a subject has been enrolled, the principal investigator is responsible for notifying Independent Ethics Committee (IEC)/Independent Review Board (IRB) regulatory authorities (as applicable), and the following AbbVie Clinical Contacts:

Primary Contact:

[name]
[name]
USA

Office:

Fax:

Alternate Contact:

[name]
France

Office:

Fax:

Such contact must be made as soon as possible to permit a review by AbbVie to determine the impact of the deviation on the subject and/or the study.

For the purposes of this protocol, reportable deviations are defined as:

- Subject entered into the study even though she/he did not satisfy entry criteria
- Subject who developed withdrawal criteria during the study and was not withdrawn

- Subject who received wrong treatment or incorrect dose
- Subject who received excluded or prohibited concomitant treatment

8.0 Statistical Methods and Determination of Sample Size

8.1.1 Analysis Population

The primary and secondary efficacy endpoints will be analyzed for the intent-to-treat (ITT) population, defined as all subjects who were randomized and received at least one dose of study medication. Subjects in the ITT population will be analyzed according to the treatment group they were randomized to. In order to evaluate the impact of major protocol violations on the results of the trial, additional analysis of the primary efficacy endpoint may be conducted on the per protocol population if deemed necessary. The Per Protocol population consists of all ITT subjects who entered the randomized period of the study and did not meet any major protocol violation during the Part 1 of the study.

The safety population consists of all subjects who received at least one dose of study medication.

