5.0 Investigational Plan

5.1 Overall Study Design and Plan: Description

This interventional Phase 4 open-label, randomized, controlled, parallel-group, multicenter study will be conducted in two (2) parts, each of 16-week duration.

Part 1 (Day 1-Week 16) is designed to compare the achievement of MDA on adalimumab introduced in combination with MTX versus MTX alone escalated to the highest recommended dose of 20-25 mg ew^{11,27} or highest tolerable dose up to 25 mg ew, whatever feasible, in PsA subjects inadequately controlled after the initial course of MTX at 15 mg ew. Part 1 will be open-label, randomized, controlled, parallel group.

Part 2 (Week 16-32) is to evaluate the effectiveness of four (4) different treatment regimens consisting of adalimumab and/or MTX in maintaining or attaining MDA, as applicable. Part 2 will be open-label, parallel group. Subjects will be assigned into the four treatment arms based on their MDA status at Week 16 and initial randomized treatment. Starting at Week 24, there will be rescue treatment option based on not achieving MDA and investigator's judgment.

Eligible male and female subjects with PsA will be selected to participate in the study according to the selection criteria.

The study will enroll approximately 240 subjects at approximately 60 sites to meet the scientific and regulatory objectives without enrolling an undue number of subjects in alignment with ethical considerations. Therefore, if the target number of subjects has been enrolled, there is a possibility that additional subjects in screening will not be enrolled.

Following a screening period of up to 30 days, subjects meeting the selection criteria will be randomized in a 1:1 ratio to either of the two (2) arms and treated for 16 weeks in Part 1:

- Arm 1/Part 1: Adalimumab 40 mg eow in combination with MTX 15 mg ew (ADA 40 mg eow + MTX 15 mg ew),
- Arm 2/Part 1: MTX escalated to 20-25 mg or highest tolerable dose ew (MTX 20-25 mg or highest tolerable dose ew).*

* MTX will be escalated by increments of 5.0 mg every 2 weeks, starting at 20 mg ew as the first MTX dose on or after Day 1, depending on the subject's MTX administration schedule prior to the study. In the case of

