5.1.2 Treatment Period

5.1.2.1 Part 1 (Randomized Open Label Treatment Period)

At the Baseline visit, subjects who meet all the inclusion criteria and none of the exclusion criteria described in Section 5.2.1 and Section 5.2.2 will be enrolled into the study and randomized in a 1:1 ratio to Arm 1 or Arm 2 of Part 1 (as described in Section 5.1). During this period of the study, subjects will visit the study site at Week 2, Week 4 and then monthly through Week 16 (if local requirements ask for additional safety assessments, e.g., due to MTX treatment, respective laboratory tests should be done locally). A \pm 2-day window is permitted around scheduled study visits.

IRT will be utilized to dispense the appropriate study drug (adalimumab and MTX) to subjects for administration during the visit or at the regularly scheduled day for MTX. Subjects will be given dosing instructions and a dosing diary at the Baseline visit.

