For subjects that cannot/will not self-administer study medication(s) or do not have adequate support (friend, family member or healthcare professional) at home, administration will occur in the clinic.

On those days that a study visit takes place, study medication is to be administered after all clinical assessments including questionnaires, ultrasound evaluation (if applicable) and vital sign determination.

Adalimumab should be administered sc at approximately the same time of the day eow or ew, as per study protocol (with the exception of office visits). At all office visits, subjects should be observed after study drug administration until judged clinically stable by the study personnel. Study drug should be administered after all clinical assessments including questionnaires and vital sign determination. If an anaphylactic reaction or other serious allergic reaction occurs, administration of study medication should be discontinued immediately and appropriate therapy initiated. When dosing at home, subjects should be instructed to contact the site immediately with any signs or symptoms of a reaction. (See Section 6.1.7 for toxicity management).

MTX should be administered orally or sc at approximately the same time of the day ew. During the study subjects should continue with their regular MTX administration schedule prior to the study enrolment. If MTX is not routinely taken on the day of the study visit, the MTX will be dispensed to the subject and the subject will take the medication home and administer it at their regular schedule. There is no relation between the adalimumab and MTX administration schedule defined per this study protocol, but generally adalimumab and MTX are not recommended to be administered on the same day. See Section 5.5.1 Treatments Administered for additional information on MTX administration and dose escalation of MTX.

For subjects who deviate from the dosing schedule, every effort should be made to bring the subject back to the study Part 1 or 2 dosing schedule as soon as possible.

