5.5 Treatments

5.5.1 Treatments Administered

5.5.1.1 Adalimumab

Adalimumab will be administered in this study open-label and at the standard dosing regimen 40 mg sc eow except in one arm of Part 2 as described below.

- Subjects randomized to Arm 1/Part 1 or assigned to Arms 1 and 4 of Part 2 at Week 16 (as described in Section 5.1 and Table 2), will receive adalimumab 40 mg eow. Starting at the Baseline (Day 1) visit, subjects who are eligible for randomization will receive the first dose of study drug: adalimumab 40 mg/0.8 mL.
- Subjects assigned to Arm 2/Part 2 (as described in Section 5.1 and Table 2), will receive adalimumab 40 mg ew beginning at the Week 16 visit.
- Subjects entering the rescue arm at or after Week 24 will have adalimumab introduced or escalated at the Investigator's discretion. For the recommended rescue treatment regimens see Section 5.1 Overall Study Design and Plan: Description.

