5.5.5 Blinding

This study is open-label study. Blinding is not applicable.

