4.7 Missing Data Imputation

The following missing data imputation will be performed for efficacy analysis.

Non-Responder Imputation (NRI) Approach

To account for missing data for the binary efficacy endpoints, a non-responder imputation approach (NRI) will be used, e.g., subjects who have missing data at a specific visit will be treated as non-responder for that visit, or who prematurely discontinue or have been rescued will be considered as a non-responder for all subsequent visits.

Mixed-Effects Model Repeated Measures (MMRM)

The repeated measure analysis will be conducted using mixed models based on observed data at all visits. For the MMRM analysis (of continuous variables), data collected after premature discontinuation of study drug will be excluded. The mixed model includes treatment, visit, treatment-by-visit interaction, and the stratification factor of duration of prior MTX use (≤ 3 months or > 3 months) as fixed effects, subject as random effect and baseline measurement as a covariate. An unstructured variance covariance matrix will be used. The parameter estimations assume data being missing at random (MAR) and using the method of restrictive maximum likelihood (REML).

Observed Cases (OC)

The OC analysis will not impute values for missing evaluations, and thus a subject who does not have an evaluation on a scheduled visit will be excluded from the OC analysis for that visit. In addition, OC will not include values after subject have rescue visit or after premature discontinuation of study drug.

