5.0 Analysis Populations and Important Subgroups

5.1 Analysis Populations

Intent-to-Treat Population Part 1

The Intent-To-Treat Part 1 (ITT Part 1) population comprises all subjects who were randomized and received at least one dose of the study medication during the Part 1 period. The data collected up to Week 16 will be included and analyzed by the treatment

group assignment given at the time of randomization, even if the subject does not receive the correct treatment, is not compliant to the protocol procedures, or does not follow the protocol until completion.

Intent-to-Treat Population Long Term

The Intent-To-Treat Long Term (ITT LT) population comprises all subjects who entered Part 2 period and received at least one dose of Part 2 study medication. The data collected from randomization and up to Week 32 will be included and analyzed by the four treatment regimens as follows:

- ADA 40 mg eow + MTX 15 mg ew/ADA 40 mg eow
- ADA 40 mg eow + MTX 15 mg ew/ADA 40 mg ew + MTX 15 mg ew
- MTX 20 - 25 mg or highest tolerable dose ew
- MTX 20 - 25 mg or highest tolerable dose ew/ADA 40 mg eow + MTX 20 - 25 mg or highest tolerable dose ew

Per Protocol Population

In order to evaluate the impact of major protocol violations on the results of the trial, additional analysis of the primary effectiveness variable may be conducted on the per protocol population, which consists of all ITT Part 1 subjects who entered the randomized period of the study and did not meet any major protocol violation during the Part 1 of the study. The determination of major protocol violation will be finalized prior to the final database lock.

Safety Population Part 1

The Safety population Part 1 consists of all subjects who received at least one dose of the study medication during the Part 1 period. The data collected up to Week 16 will be included and analyzed by the two "As treated" treatment groups in Part 1. "As treated" is determined by the treatment a subject received during majority of the subject's drug exposure time in the analysis period, regardless of the treatment randomized.

Safety Population Part 2

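### The set called intent-to-treat excludes randomised subjects who never dose; in this open-label trial that exclusion can depend on arm, and no analysis of all randomised subjects is planned

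*Protocol*

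**What the plan says.** The protocol synopsis and Protocol 8.1.1 define the intent-to-treat population as "defined as all subjects who were randomized and received at least one dose of study medication". SAP 5.1 carries this into its Part 1 set, which "comprises all subjects who were randomized and received at least one dose of the study medication during the Part 1" period. SAP 6.1 takes the key efficacy findings from that set. Subjects in the set are analysed in the arm to which they were randomised.

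On blinding, Protocol 5.5.5 states: "This study is open-label study. Blinding is not applicable".

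On the first dose, the arms differ:

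- **Adalimumab arm.** Protocol 5.5.1.1 says that at the Day 1 visit "subjects who are eligible for randomization will receive the first dose of study drug: adalimumab 40 mg/0.8 mL".
- **Methotrexate arm.** Protocol 5.1 describes escalation "starting at 20 mg ew as the first MTX dose on or after Day 1". Protocol 5.1.2.1 has drug dispensed "for administration during the visit or at the regularly scheduled day for MTX". Protocol 5.3.1.1 adds: "If MTX is not routinely taken on the day of the study visit, the MTX will be dispensed to the subject", who then takes it at home on the usual day.

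Two other analyses of the primary endpoint are named: a sensitivity analysis on observed cases (Protocol 8.1.4.1, SAP 6.2), and an optional per-protocol analysis on a subset of the same dosed set (Protocol 8.1.1, SAP 5.1).

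**The concern.** An intent-to-treat comparison keeps everyone who was randomised, because only the groups as randomised are protected from selection. Requiring a dose adds an event after randomisation as a condition of entry. In a blinded trial that can be defended, since subject and site do not know the arm when the decision to start is made. Here they do know it.

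The opportunity to leave undosed also differs by arm. A subject allocated to more of a drug that has already proved inadequate may go home with it and not return. Someone allocated to adalimumab is dosed at the visit. Any exclusion can therefore depend on arm, and analysing the remaining subjects as randomised does not undo it.

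At stake is whether the result reported as intent-to-treat is one, and whether a reader could check. Disposition counts by arm (Protocol 8.1.6) would show how many were lost. They would let a reader rebuild the crude rate, but not the stratified Cochran-Mantel-Haenszel (CMH) result.

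**Working it through.** **Inputs.** Response rates of 40% and 20%, 120 per arm, two-sided 0.05 and 10% dropout come from Protocol 8.2 and SAP 4.4. The number of undosed subjects is in neither document. I assume k = 2, 6 or 10 of 120 in one arm only, all non-responders. The tests below are unstratified, with pooled variance; the planned CMH test is stratified by duration of prior methotrexate.

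**The plan's own figure.** The pooled two-proportion formula without continuity correction needs 109 per arm for 90% power. Power is 92.7% with 120 per arm and 89.9% with 108 (120 less 10%). The stated sample size reproduces to rounding and is not in dispute.

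**Effect on the estimate.** The planning rates give 48/120 and 24/120, a difference of 20.0 points. Dropping k undosed non-responders changes one denominator to 120 − k.

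| Undosed arm | k | Adalimumab | Methotrexate | Difference (points) | Change (points) |
|---|---|---|---|---|---|
| none | 0 | 48/120 = 40.0% | 24/120 = 20.0% | 20.0 | – |
| methotrexate | 2 | 40.0% | 24/118 = 20.3% | 19.7 | −0.3 |
| methotrexate | 6 | 40.0% | 24/114 = 21.1% | 18.9 | −1.1 |
| methotrexate | 10 | 40.0% | 24/110 = 21.8% | 18.2 | −1.8 |
| adalimumab | 2 | 48/118 = 40.7% | 20.0% | 20.7 | +0.7 |
| adalimumab | 6 | 48/114 = 42.1% | 20.0% | 22.1 | +2.1 |
| adalimumab | 10 | 48/110 = 43.6% | 20.0% | 23.6 | +3.6 |

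**Effect on the test.** z = (p1 − p2) / √[p(1 − p)(1/n1 + 1/n2)], where p is the pooled rate.

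- All randomised, 48/120 v 24/120: z = 0.200 / √(0.30 × 0.70 × 2/120) = 3.38, p = 0.0007.
- Ten methotrexate subjects dropped, 48/120 v 24/110: z = 2.97, p = 0.0030.
- Ten adalimumab subjects dropped, 48/110 v 24/120: z = 3.86, p = 0.0001.

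**Near the threshold.**

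- 38/120 v 24/120: z = 2.06, p = 0.039. With 6 methotrexate subjects dropped (24/114): z = 1.84, p = 0.066. With only 2 dropped (24/118): p = 0.047, still below 0.05.
- 37/120 v 24/120: z = 1.93, p = 0.054. With 2 adalimumab subjects dropped (37/118): z = 2.01, p = 0.045.

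**Type I error.** Suppose the true rate is 30% of all randomised in both arms, and 2, 5 or 10 non-responders are removed from one arm. By normal approximation the two-sided error is about 5.1%, 5.5% or 7.3% instead of 5.0%.

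**Is the exclusion needed?** SAP 4.7 already states that "subjects who have missing data at a specific visit will be treated as non-responder for that visit", so an undosed subject with no Week 16 data has an outcome. Protocol 5.5.3 fixes the stratum at randomisation. Both inputs to the CMH test exist for every randomised subject.

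**The case against.** The strongest reply is about weight, and much of it stands.

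- The rule is stated openly and consistently, and the randomised and dosed counts are tabulated by arm. That is true. It makes the loss visible without supplying the comparison.
- Exclusions should be few. Protocol 5.3.1.1 has the first dose follow the other Day 1 procedures, home dosing arises only when the usual methotrexate day is not the visit day, and the gap is less than a week in people already taking the drug. This stands as a limit on size. Ten in one arm and none in the other is the far end of an assumed range.
- The only arm-specific mechanism in the text, delayed methotrexate dosing, works against adalimumab. This stands. No passage suggests why the adalimumab arm would lose subjects before dosing, so the widening figures illustrate the other direction and are not a forecast.
- The near-threshold examples are chosen. This also stands. With 24/120 on methotrexate and 33 to 43 adalimumab responders, dropping 2 methotrexate subjects never crosses 0.05, and dropping 2 adalimumab subjects crosses it only at 37.
- Baseline is tied to the first dose (Protocol 8.1.2) and so is undefined for the undosed. This does not stand. Day 1 assessments precede dosing, and baseline is the last pre-treatment value up to Day 1, so it exists for anyone who attended that visit.

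**Conclusion.** The concern holds. The primary set is a modified intent-to-treat set under another name, arm is known before the dose that decides membership, and no analysis of all randomised subjects is planned. The likely effect is small. With nobody undosed it is zero; with 2 to 10 undosed in one arm it is −0.3 to −1.8 or +0.7 to +3.6 points at the planning rates, with no change in conclusion there. Only a result close to 0.05 could change. These figures rest on the assumed k, on the undosed being non-responders, and on unstratified tests. Because the exclusion is not needed to run the primary test, the change should be made.

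A separate, minor point concerns the optional per-protocol analysis. SAP 5.1 lets major violations be settled up to the final lock, whereas the Week 16 result comes from the earlier Part 1 lock (SAP 4.5). Violations may, though they need not, be classified with the primary result known.

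**What to change.** In the protocol synopsis, Protocol 8.1.1, SAP 5.1 and SAP 6.2:

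1. Analyse the primary and binary secondary endpoints in all randomised subjects, in the arm assigned, with undosed subjects as non-responders under the existing imputation rule.
2. Keep the dosed set as a supportive analysis labelled modified intent-to-treat, and keep it for safety.

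In SAP 5.1, Per Protocol Population, set the deadline for classifying major violations to the Part 1 database lock.

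The cost is wording only. Arm and stratum are known for everyone randomised, so no data are added. Response rates may be marginally lower. The repeated-measures analyses do not change, because subjects with no post-baseline data contribute nothing to them.
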